15.3. SUMMARIES FOR WOUND CLOSURE

The wound closure(yes/no), closure method and definitive wound closure method will be summarized by treatment. the information of wound closure will be listed. The chi-square test will be used to test the differences between two groups, p-value will be presented.

15.4. SUMMARIES FOR SUBJECTS RECEIVED TREATMENT

The number of days subjects received treatment and number of dressing changes will be listed and summarized by treatment group. The Wilcoxon rank-sum test will be used to test the differences between two groups, p-value will be presented.

15.5. SUMMARIES FOR NPWT APPLICATION

The application time (minutes) for each dressing change, any leaks and treatment settings will be listed and summarized by treatment group.

16. Exploratory endpoints

An exploratory analysis will be conducted on the exploratory endpoints (volume, area and granulation tissue) using the FAS. Listings will be presented and sorted by treatment group, subject id.

Repeated measure analysis of variance using mixed model on mean change in exploratory endpoints(volume, area and granulation tissue) at each dressing change time point as dependent

Analysis Plan

Protocol No.: KCI.VERAFLO.2018.02

variables with center, treatment group and treatment-by-center interaction as fixed factors, wound size (wounds surface area, $<15\text{cm}^2$ (ref), $15\text{-}30\text{cm}^2$, and $>30\text{cm}^2$) as covariate, and time point as repeated factor will be performed using mixed model. The P-value of center, treatment group, treatment-by-center interaction, wound size and time point will be reported. LS Means and LS Mean difference and P-values for LS Mean difference will be reported out for each visit.

Above statistical analysis method will be conducted on wound area.

An example of SAS code is provided:

```
Proc mixed DATA=xxx covtest metood=ml;
Class id treat center woundtype timepoint;
Model volume(or area,or granulation tissue)=treat center treat*center woundtype timepoint
/htype=3 s noint;
Repeated timepoint/type=sample (covariance structure may be TOFL, AR(1) or UN. Likelihood
ratio testing (LRT) may be used to select best fitting model
Subject=id(treat);
Run;
```

17. Evaluation of Safety

All outputs for safety outcomes will be based on safety set, and presented by treatment groups.

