### **5.2 Selection of Subjects**

#### **5.2.1 Inclusion Criteria**

Only adult subjects meeting all of the following criteria to be considered for participation:

- (1) Subject voluntarily participate in the trial and sign the informed consent form, and is willing to comply with protocol and all visits
- (2) Is anticipated to be an inpatient for a minimum of 6 days
- (3) Age: between 18 years and 70 years
- (4) Patient with open wounds from various etiologies with extensive soft tissue damage after definitive surgical debridement and appropriate for NPWT
- (5) The minimum size of the wound as measured by 3D wound imaging prior to entry into the study is 8cm (in any dimension), minimum 1cm in width and 0.8cm in depth. i.e. the minimum wound size is 8cm×1cm×0.8cm. Only one wound per subject will be included in the study, regardless of how many wounds the subject

has.

- (6) Female subjects of reproductive potential must have a negative pregnancy test result and must not be lactating at the screening visit.
- (7) Subject must be willing and able to use a highly effective contraception method during study participation.

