### **5.2.2 Exclusion Criteria**

Subject who meets any of the following criteria will be excluded from participation in the study:

- (1) Subject undergoing chemotherapy
- (2) Subject with known immunodeficiency
- (3) Subject with serious complications or serious systemic infection
- (4) Known bleeding disorder or has received or is planning to receive long-term anticoagulation therapy
- (5) Known allergic reactions/hypersensitivity to any of the study treatment dressings components
- (6) Target wound is a burn wound
- (7) A wound open for 6 months or more
- (8) The subject's targeted traumatic wound injury is a craniofacial wound
- (9) There is implant (such as cardiac pacemaker, bone nail, bone lamella, artificial joint, artificial bone) visible in the targeted wound.
- (10) If undermining or tunneling represents approximately 15% or more of the wound.
- (11) A wound with enteric fistulas.
- (12) Subject's targeted wound that is contraindicated with investigational device including:
  - a) Malignancy in the wound
  - b) Untreated osteomyelitis
  - c) Non-enteric or unexplored fistulas
  - d) Necrotic tissue with eschar remaining in the wound after surgical debridement

(once necrotic tissue or eschar is removed from the wound bed, subjects may be included)

- e) Unprotected, exposed blood vessel, anastomotic sites, organs, or nerves in direct contact with foam
- f) Thoracic or abdominal cavities
- g) Unexplored wounds that may communicate with adjacent body cavities

(13) Subject's targeted wound that is contraindicated with the control group device and not suitable for participating in the trial judged by investigator

(14) Participation in another device or drug study within the past 30 days before screening or during study participation

(15) Other subjects who are not suitable for participating in the trial judged by investigator.

(16) Wounds that require more than 2 images in order to capture the entire wound.  
NOTE: each image must not exceed 20 cm in any one direction.

(17) Wound presents on greater than 50% of the circumference of any part of the body (e.g. wound that wraps around >50% of a leg or arm).

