### **Exploratory endpoints**

Repeated measure analysis of variance using mixed model on mean change in exploratory endpoints (volume, area and granulation tissue) at each dressing change time point as dependent variables with site, treatment group and treatment-by-site interaction as fixed factors, wound size (wounds surface area,  $<15\text{cm}^2$ ,  $15\text{-}30\text{cm}^2$ , and  $>30\text{cm}^2$ ) as covariate, and time point as repeated factor will be performed using mixed model.

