7.6. COMMON CALCULATIONS

For quantitative measurements, change from baseline will be calculated as:

- Test Value at Treatment Interval X – Baseline Value

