15.1.3. PRIMARY ANALYSIS OF PRIMARY EFFICACY VARIABLES

PPS population is the primary efficacy analysis population. Descriptive statistics of actual wound volume, wound volume changes (wound volume before study treatment –wound volume of each visit) and wound volume reduction rate at visit (wound volume before initial study treatment –wound volume at visit)÷wound volume before initial study treatment×100% by visits, treatment group and overall will be provided.

Listings of actual wound volume will be presented and sorted by subject id, treatment group and visit.

The statistical hypothesis for testing the treatment group difference for primary efficacy endpoint is presented as follows:

- $H_0: M_T - M_C \leq -0.20$ tested against the alternative hypothesis
- $H_1: M_T - M_C > -0.20$

where:

M_C is the means in control group and M_T is the means in to V.A.C. VERAFLTM group.

A two-sided 95% confidence interval for $M_T - M_C$ will be constructed using the method of ANCOVA with treatment group, center, and treatment-by-center interaction (if the interaction effect is not statistically significant, then it will be removed from the final model) as fixed factors, and wound size (wounds surface area, <15cm² (ref) , 15-30cm², and >30cm²) as covariate.

The following statistics will be presented: LS Means, difference of the LS Means as well as its two-sided 95% CI, p-value for LS Mean difference. If the lower limit of the two-sided 95% confidence interval of difference is greater than -0.20, then it will be concluded that the V.A.C. VeraFloTM Dressing Kit is non-inferior to the approved control dressing in China (Local) + wall suction.

A rejection of the null hypothesis will trigger superiority testing based upon treatment difference. If the lower limit of the CI is greater than zero, V.A.C. VERAFLTM Dressing Kit is proven to be superior to control dressing.

The two hypothesis tests are hierarchically structured so that the second test (superiority) will only be considered if the first test (non-inferiority) is rejected. There is no alpha adjustment for the second test

as a result of the hierarchical testing.

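### The exploratory over-time model uses an absolute scale for wound volume and area, so it weights large wounds more heavily than the percent-reduction endpoints do

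*SAP*

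**What the plan says.** Protocol 6.5.1 (Exploratory endpoints) plans a "Repeated measure analysis of variance using mixed model on mean change in exploratory endpoints". SAP 16 repeats this on the FAS, with dependent variables "mean change in exploratory endpoints(volume, area and granulation tissue) at each dressing change time point". SAP 7.6 defines change from baseline as "Test Value at Treatment Interval X – Baseline Value".

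SAP 15.1.3 lists the absolute and relative quantities separately, for description by visit: "wound volume changes (wound volume before study treatment –wound volume of each visit) and wound volume reduction rate at visit". SAP 15.2.3 does the same for area.

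The example code in SAP 16 reads "Model volume(or area,or granulation tissue)=treat center treat*center woundtype timepoint". The left side is the raw value, not the change. Neither text nor code has a continuous baseline volume or area term. Size enters only as three surface-area classes (<15, 15-30 and >30 cm²), the last one open-ended. There is no treatment-by-timepoint term, although LS mean differences are promised for each visit.

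The primary endpoint (SAP 15.1.1) and the wound area endpoint (SAP 15.2.3) are percentages of the baseline value.

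**The concern.** The range of eligible wound sizes is wide. Protocol 5.2.1 states that "the minimum wound size is 8cm×1cm×0.8cm", which is 8 cm² and, as a box, 6.4 cm³. Protocol 5.2.2 allows up to two images, and "each image must not exceed 20 cm in any one direction", so the geometric ceiling on area is 2 × 20 × 20 = 800 cm².

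If shrinkage is roughly proportional to size, absolute change equals baseline volume times reduction rate, and its SD rises with baseline volume. The mixed model assumes one covariance structure for all subjects. Area strata shift the mean but leave this unequal variance in place. A minimum-size wound that fills by half contributes 3.2 cm³. A wound of 200 cm³ (an illustrative size, not from the documents) that does the same contributes 100 cm³, about 31 times as much. In the primary analysis both count as 50%.

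At stake is the only planned model of the by-visit course. On its present scale it answers a different question from the primary endpoint, and may do so with less precision.

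**Working it through.** **1. The plan's own figure.** The documents give no precision for the exploratory model, only the sample size for the percent-scale primary endpoint. With margin 0.20, SD 0.40 and one-sided 0.025 (Protocol 6.1.1, SAP 5.4):

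n per arm = 2 × (1.960 + 0.842)² × 0.40² / 0.20² = 62.8, so 63 by the normal approximation.

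The noncentral t gives power 0.795 at 63 and 0.801 at 64. The stated 64 per arm (128 evaluable) is reproduced. The 40% SD is used below.

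**2. Formula for the loss.** Let V be baseline volume with coefficient of variation cv, and R the reduction rate with mean μ and SD σ = 0.40. Let R be independent of V, and the treatment effect constant in percent. The efficiency of analysing V × R, relative to R, is

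RE = σ² / [σ² + cv²(μ² + σ²)].

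If baseline volume is fully adjusted for in the mean, the μ² term drops out and RE = 1/(1 + cv²). For log-normal V with log-SD s this equals exp(−s²). The value of s is an assumption. The last column is the share of subjects carrying half of the variance, 1 − Φ(2s).

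| s (assumed) | cv | Loss, 1 − exp(−s²) | Loss, no size adjustment, μ = 0.4 | Share of subjects with half the variance |
|---|---|---|---|---|
| 0.5 | 0.53 | 22% | 36% | 16% |
| 0.7 | 0.80 | 39% | 56% | 8% |
| 0.9 | 1.12 | 56% | 71% | 4% |
| 1.1 | 1.53 | 70% | 82% | 1% |

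**3. Is that range of s plausible?** The cut-points of 15 and 30 cm² give a rough guide for area, if area is log-normal. If the strata fill 25/50/25, s = ln 2 / (2 × 0.674) = 0.51 (loss 23%). If they fill in thirds, s = ln 2 / (2 × 0.431) = 0.80 (loss 48%). Expected stratum fill is not stated, so this shows plausibility only.

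**4. Simulation with size adjustment.** These runs use one time point and 64 per arm.

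- *Area strata plus continuous baseline volume* (mean reduction 45% in control, 20-point effect, rate capped at 100%). Simulated power was 77-79% on the percent scale, against 69%, 58%, 51% and 41% on the absolute scale for the four values of s. Converting by [(z_power + 1.96)/(z_0.78 + 1.96)]² gives losses of about 19%, 37%, 47% and 60%.
- *Area strata only, as the plan has it* (μ = 0.2 to 0.4). The loss was 16-20% at cv 0.37, 35-44% at cv about 0.63, 59-68% at cv about 1.03 and 69-75% at cv 1.24. With raw volume on the left side, as in the example code, it ran from 20-26% at the smallest cv to 76-85% at the largest.

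**5. If percent reduction is noisier in small wounds.** Again with area strata only: if the percent SD is proportional to V^−0.25, the loss is 4-68%. If it is proportional to V^−0.5, the result runs from a 14% gain to a 60% loss.

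**The case against.** **Magnitude.** No baseline size distribution is given, so any loss figure rests on an assumed spread, a constant percent SD and an effect constant in percent. This stands. A reader might infer that 20-70% of the information is lost as a fact; the documents do not support that. Percent change can be noisy in small or shallow wounds, and the exclusion rules for the PPS themselves anticipate unreliable depth. If the SD falls as V^−0.5 and a continuous baseline volume term is added, which the plan does not have, the absolute scale was more efficient in every simulated case. The percent scale is therefore justified mainly by agreement with the trial's own endpoints, not by guaranteed efficiency.

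**A few large wounds.** A reader might infer that a handful of subjects set the treatment difference. That fits only strong skew. At s = 0.5, about 16% of subjects (some 20 of 128) carry half of the variance.

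**Power.** A reader might restate the loss as lost power at 64 per arm. That is the evaluable number for the PPS. This model uses the FAS with repeated visits, up to 170 subjects may be randomised, and no power is claimed for it.

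**Is the scale really absolute?** The documents also describe the percent endpoint as a change over 14 days, Protocol 6.5.1 speaks of mean change in wound area reduction rate, and under SAP section 8 the output templates override the SAP text. Still, SAP 7.6, the separate listing in SAP 15.1.3 and the example code all point to an absolute scale. The remaining doubt is a reason to state the scale.

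**Consequence.** The percent rates are already reported descriptively by visit, and the model has no success criterion. This stands and limits the priority.

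**Conclusion.** The point holds as a minor one. The over-time model is on an absolute scale (change by the text, raw value by the code), while the primary and area endpoints are percent reductions. If wounds shrink roughly in proportion to size, larger wounds get more weight, and three area strata with an open top class do not remove this.

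The loss is about 20-70% by formula and about 20-60% in simulation with size adjustment. Both figures assume log-normal baseline volume with log-SD 0.5 to 1.1 and a percent SD of 40% at all sizes. The loss is smaller, or could become a small gain under the plan's strata adjustment, if small wounds are noisier in percent.

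A reader might go further and infer that the time course will contradict the primary result, or that the non-inferiority conclusion is at risk. The documents do not support either. Divergence is possible but was not shown to occur. The primary analysis, the margin and the sample size are untouched. Granulation tissue is outside this point.

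**What to change.** In SAP 16 and the matching paragraph of Protocol 6.5.1:

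- Make the dependent variables the by-visit volume and area reduction rates already derived in SAP 15.1.3 ("wound volume reduction rate at visit") and SAP 15.2.3.
- Make the example code use the same variable as the text.
- Add a treatment-by-timepoint term. Without it the model yields one common treatment difference, not the promised difference at each visit, so changing the left-hand variable alone would not show when the arms separate.
- Keep wound size as covariate.
- Report changes in cm³ and cm² descriptively, as SAP 15.1.3 and 15.2.3 already do.
- Align the output templates, since they take priority over the SAP text.

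The cost is SAP and protocol wording, one changed variable and one added model term. It is cleanest before database lock. The small downside is that the model estimate is no longer in cm³ or cm².

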#### **5.1.2.4 Rationale of Blinding Selection**

This trial is set as open label, since the inconsistent packaging appearance of the devices between the two groups, the investigators and the subjects could not be blinded.

In this trial, independent assessors will be blinded to reduce measurement bias from outcome indicator measurers. 3D images collected from each site will be aggregated into a single database. The aggregated images will be analyzed / measured by the independent assessor so as to achieve the blinding of independent assessors.

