#### **5.5.3 Specification Direction for Use of Device**

- (1) For subjects with multiple wounds, the target wound can only be treated with the randomly assigned device and the other wounds will receive the standard wound treatment in the institution.
- (2) Placing the dressings in the target wound directly following the definitive surgical debridement (if applicable) according to the investigational or control device IFU.
- (3) During the subject's hospital admission, subjects will receive their assigned study

treatment without interruption until the wound is deemed ready for closure or up to 14 days (whichever occurred first).

- (4) For the investigational group, instillation solution (only normal saline) will be refilled by related staff as often as required. Canister changes for each group will be performed by related staff as often as required.
- (5) Dressing change frequency will be determined by the investigator based on the wound condition and clinical experience, and the frequencies of investigational and control group devices are the same (48-72h one change).
- (6) If the wound has been deemed ready for closure, study treatment will stop and subjects will then transition to receive institutional standard wound treatment at the discretion of the investigator.
- (7) If the secondary intervention condition of the target wound is not met after 14 days of treatment with the investigational device, the patient will receive further clinical treatment judged by the investigator re-evaluation according to the standard wound treatment in the institution.

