7.4. WINDOWING CONVENTIONS

No visit windowing will be performed for this study

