15.2.2. TIME TO COMPLETION OF WOUND BED PREPARATION (UNIT: DAY)

Define: Duration from the randomization until target wound ready for closure by secondary intervention judged by the investigator.

Evaluation time point: Day of Randomization (Day 0) and End of Treatment Visit.

Measurement: the date deemed ready for closure by secondary intervention - the date of the randomization + 1.

Statistical method: the difference between investigational group and control group will be assessed by Kaplan-Meier method and log rank test, and with covariate adjustment using the Cox proportional hazard regression and Wald Chi-Square.

Censor data define: .

The duration of treatment for a patient is considered right-censored if it meets one of the below conditions:

- Patient completed the study but the completion category was “The treatment duration up to 14 Days”, and the subjects’ target wound not ready for closure before end of treatment visit. Patient’s will be censored on day of end of treatment visit.
- Patient prematurely withdraws from the study and the subjects’ target wound not ready for closure before end of treatment visit, patients will be censored on the date of their last 3D wound imaging assessment.
- Subjects with no post-baseline 3D imaging wound measurements assessments will be censored on the day of randomization (i.e. Day 0).

Here, duration of treatment for a patient is defined as the date of the last wound measurements assessments minus the date of randomization plus one.

The Kaplan-Meier analysis of the time to completion of wound bed preparation will be performed, the Kaplan-Meier plot will be presented. The Cox proportional hazard regression with covariates from primary endpoints will be used to estimate the hazard ratios for effect of treatment factor.

The results of the log-rank test for the comparison of investigational group and control groups will be expressed by a Chi-square statistic and P-value, The results of cox proportional hazard regression will be present by HR statistic and P value, the P-value <0.05 will be considered as statistically significant.

An example of SAS code for cox proportion regression model is provided:

```
Proc phreg;
Class treat(ref=control) center(ref=sitel1) woundtype(ref=1);
Model time*completion of wound bed preparation(yes) =treat center treat*center woundtype
/risklimits;
Run;
```

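### The exploratory over-time model and the by-visit tables count time in dressing changes, and change k can fall anywhere from Day 2k to Day 3k; actual treatment days should be used

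*SAP*

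**What the plan says.** - **Time axis of the model.** SAP 16 fits a repeated-measures mixed model to "exploratory endpoints(volume, area and granulation tissue) at each dressing change time point as dependent" variables, and Protocol 6.5.1 likewise works "at each dressing change time point as dependent variables". In the SAP's example code the time point is a class variable and no study-day term appears. The text promises LS-mean differences with p-values for each visit.
- **By-visit tables.** Volume (SAP 15.1.3), area (SAP 15.2.3) and the clinical assessments (SAP 15.2.4) are summarised by visit. SAP 7.3 uses the nominal visit and gives early-termination data the next visit's number. SAP 7.4 states: "No visit windowing will be performed for this study".
- **Study Day.** SAP 7.1 defines it from the first device application, but only to show when assessments and events start and stop.
- **Schedule.** Protocol 5.5.3 (5) says "Dressing change frequency will be determined by the investigator based on the wound" condition and clinical experience, and that "the frequencies of investigational and control group devices are the same (48-72h one change". Protocol 5.5.2.3 has the date and time of each change recorded.
- **Blinding.** Protocol 5.1.2.4: "This trial is set as open label". Only the image assessors are blinded.
- **Time to readiness.** SAP 15.2.2 works from calendar dates: "the date deemed ready for closure by secondary intervention - the date of the randomization + 1".

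**The concern.** A dressing-change number is an order, not a duration. Two subjects at change 4 may have had 8 and 12 days of treatment, and neither has deviated from the protocol. A difference between arms at that change could then reflect how long the wounds had been treated rather than how fast they were healing. The stated equality of frequency gives both arms one shared range; it does not fix an interval within that range. The person who chooses the interval knows the allocation and bases the choice on wound condition, which is close to what the model measures. Blinded image reading protects the measurement but not its timing.

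What is at stake is the reading of the exploratory trajectories and the by-visit tables, not the confirmatory conclusion.

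**Working it through.** The documents give no figure for the spread of treatment days at a dressing change, so there is none to reproduce.

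**1. Permitted range.** Inputs: interval 48 to 72 h (Protocol 5.5.3) and treatment up to 14 days (Protocol 5.1.1). Change k falls between 48k h and 72k h, that is 2k to 3k days after first application.

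| Change k | Earliest day | Latest day | Spread (days) |
|---|---|---|---|
| 1 | 2 | 3 | 1 |
| 2 | 4 | 6 | 2 |
| 3 | 6 | 9 | 3 |
| 4 | 8 | 12 | 4 |

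The relative spread is the same at every k: (3k − 2k)/2k = 50% of the shorter time, or (3k − 2k)/3k = 33% of the longer. By Day 14 a 48 h schedule allows 14/2 = 7 changes. A 72 h schedule allows 4, because a fifth would fall on Day 15.

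**2. Typical spread (assumed distributions).** If every interval is drawn independently and uniformly from 2 to 3 days, change 4 falls at mean day 10.0 with SD √(4/12) = 0.58 day. If each subject keeps one interval drawn from the same range, the SD is 4 × √(1/12) = 1.15 days.

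**3. Outcome units (assumed linear reduction of R points over 14 days).** Two subjects whose intervals differ by δ days differ at change k, from timing alone, by R × k × δ/14 points. For the permitted extreme (δ = 1) at k = 4:

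- R = 20: 20 × 4/14 = 5.7 points
- R = 40: 40 × 4/14 = 11.4 points
- R = 60: 60 × 4/14 = 17.1 points

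The same formula gives the between-arm artefact if δ is the difference in mean interval between arms. With R = 40 and k = 4, a difference of 0.25 day gives 2.9 points and 0.5 day gives 5.7. If δ = 0 between arms, the artefact is zero on average and only noise remains. That noise has an SD of (40/14) × 0.58 = 1.6 to (40/14) × 1.15 = 3.3 points under the two assumptions in step 2.

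**4. Covariance.** AR(1) ties correlation to the number of changes apart and so treats changes as equally spaced. It is one of three candidates in SAP 16, to be chosen by likelihood-ratio testing; UN, also listed, makes no spacing assumption.

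**5. Readiness, a separate matter.** Suppose readiness is first seen at a dressing change, with true time exponential and median 6 days (both assumed), and Day 14 as the last look. The mean recorded time, capped at 14 days, is:

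- 48 h schedule: 2 × Σ P(T > 2j), j = 0 to 6, = 7.77 days
- 72 h schedule: 3 × Σ P(T > 3j), j = 0 to 3, + 2 × P(T > 12) = 7.68 + 0.50 = 8.18 days

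The extreme-case gap is 8.18 − 7.77 = 0.41 day. Without the cap, the mean delays are 1.04 and 1.59 days, a gap of 0.55 day, but the protocol does not allow unlimited follow-up.

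**The case against.** The strongest reply is that the protocol says twice that the two devices are changed at the same frequency (5.5.2.3 and 5.5.3). An arm changed every 48 h against an arm changed every 72 h would need that rule to fail systematically. If intervals vary by wound in both arms alike, randomisation balances baseline wound condition and the result is mostly noise. This stands: nothing in the documents shows a difference between arms.

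It is also fair to say that the model is labelled exploratory, that the visit schedule has no nominal days between baseline and end of treatment, and that SAP 15.4 already compares treatment days and number of changes by arm, from which an average interval can be worked out. These points limit the stakes. They do not put the model on a time scale, and SAP 15.4 feeds nothing into it.

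A reader might infer three stronger things that the documents do not support:

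- **That the non-inferiority result is at risk**, for instance by setting 11.4 points against the 20-point margin. The primary endpoint runs from baseline to end of treatment and uses no change number.
- **That time to readiness has the same fault.** SAP 15.2.2 uses dates. That readiness is mostly first seen at a change is a reasonable inference from the visit schedule, but no section says so.
- **That the readiness artefact equals the 6.8 versus 6.3 day result in Protocol 3.1.3.1.** That difference was not significant (p = 0.7105), is no margin here, and the capped artefact is smaller.

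**Conclusion.** The point holds for the SAP 16 mixed model and the by-visit descriptive tables, and no further. Within protocol, the same change number can carry up to 50% more treatment days in one subject than in another (Day 8 to 12 at change 4). That range follows directly from the 48 to 72 h rule and needs no assumption. Its effect on outcomes depends on an assumed linear healing rate: 5.7 to 17.1 points at change 4 between two subjects at opposite extremes, and less for typical spreads. Bias between arms arises only if the achieved intervals differ by arm, which the open-label design permits but the documents do not show. The primary test is unaffected. This is a worthwhile, inexpensive improvement to exploratory and descriptive outputs, not a threat to the trial's main conclusion.

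**What to change.** - **SAP 16.** Replace the change-number factor with actual days since first application, from the dates and times recorded under Protocol 5.5.2.2 and 5.5.2.3, either as continuous time or as day windows defined before database lock. State the day count, because SAP 7.1 numbers the first application as Day 1 and the protocol numbers randomisation as Day 0.
- **Covariance.** If time is continuous, replace AR(1) with a structure that allows unequal spacing, such as spatial power.
- **SAP 7.4, 15.1.3, 15.2.3 and 15.2.4.** Present the by-visit summaries by study-day window.
- **SAP 15.4.** Tabulate the achieved change interval by arm beside the existing summaries, so that a reader can see whether the arms differ.
- **Optional and separate, SAP 15.2.2.** Add an interval-censored sensitivity analysis bounded by the last not-ready and first ready inspection.
- **While editing SAP 16.** The example code has no treatment-by-time term, although per-visit differences are promised. This is a separate matter, best settled in the same revision.

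The cost is programming, a choice of time form or windows, and a day-based table layout. The main changes need no new data and no change to patient management.
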